# 7.7 Dietary Requirements

Multiple food effect studies have demonstrated that high fat, protein or carbohydrate meals all had a similar effect of decreasing the maximum serum concentration ( $C_{max}$ ) (average of 80-90%),

prolonging the time of maximum plasma concentration ( $T_{max}$ ) (8-12 fold), and decreasing the area under the concentration time-curves from time zero to infinity ( $AUC_{0-\infty}$ ) of ifetroban (average of 25-35%) compared to the fasting state.

For this reason, ifetroban and placebo should be taken at least 30 minutes before a meal or six hours after a meal.

#### 8 STUDY VISITS AND PROCEDURES

# 8.1 Overview – Schedule of Time and Events

This 13-Week study will consist of a three-week Screening Period (Week -3 to Week 0), an 8-week Treatment Period (Week 0 to Week 8) and a two-week Post-treatment Period (Week 8 to Week 10). The study visits occur on the planned dates relative to the first dose of IMP as scheduled. The visit schedule should be adhered to within the  $\pm$  5 day visit window.

If a subject is prematurely discontinued from treatment, all assessments planned at the End of Treatment visit should be performed. Prior to all screening assessments, after discussion of participation in the study, the written consent form must be signed and dated. Although the screening assessments for this study are grouped under the heading of a single visit in this protocol, it is possible for them to be performed over more than one site visit if necessary, as long as the three-week screening period relative to the first dose of IMP is respected. Subjects that fail screening for exclusion criteria, for example concomitant medications, acute illness (upper respiratory tract infection), required drug-specific discontinuation periods or laboratory tests, may be rescreened for study eligibility one additional time.

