# 7 STUDY DESCRIPTION

# 7.1 Study Design

[figure not shown]
CPI-IFE-006 is a randomized, double-blind, placebo-controlled Phase 2 study to evaluate oral ifetroban administered daily for eight weeks in symptomatic AERD subjects.

Approximately 76 subjects will be randomized into two treatment groups of 38 subjects per group.

The clinical study will be conducted with 3 periods:

- Screening period of up to three weeks
- Randomized ifetroban/placebo treatment period of eight weeks
- Post-treatment period for safety and efficacy of two weeks

Figure 7-1 Study Design

ACQ = Asthma Control Questionnaire; FeNO = Fractional exhaled nitric oxide; FEV1 = forced expiratory volume in one second; PBO = placebo; PD = pharmacodynamic; PNIFR = peak Nasal Inspiratory Flow Rate; SNOT = Sinonasal Outcome Test; TNSS = Total Nasal Symptom Score; UPSIT = Smell Identification Test

The total duration of the study participation for each subject is up to 13 weeks. Recruitment is planned to stop when approximately 76 subjects are randomized. The end of the study is defined as the last subject's last visit/contact.

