#### If the subject meets all inclusion and does not meet any exclusion criteria:

- Subject will be randomized
- PNIFR and FeNO will be recorded
- Perform serum/urine pregnancy test (for women of childbearing potential). Confirm subject is protected by one of the following acceptable forms of effective contraception during the study:
  - Established use of oral, injected or implanted hormonal contraceptive
  - "Double barrier" methods (i.e., Double Intrauterine device with copper or intrauterine system with progestogen and barrier contraceptive [condom, diaphragm or cervical/vault caps] used with spermicide [foam, gel, film, cream or suppository])
  - Female sterilization (e.g., tubal occlusion, hysterectomy or bilateral salpingectomy)
  - Male sterilization with post-vasectomy documentation of the absence of sperm in the ejaculate; for female subjects enrolled in the study, the vasectomized male partner should be the sole partner for that subject
- Perform blood sampling (prior to administration of IMP) for clinical laboratories: hematology, chemistry, PT, and INR.

Note: Clinical laboratory testing at Week 0 Visit is limited to biomarkers in serum and plasma if screening labs were performed within three weeks of starting IMP treatment.

- Collect urine and blood samples for eicosanoid metabolites.
- Collect nasoabsorptive matrix for eicosanoid measurements.

- Conduct a smell test (UPSIT)
- Collect data from subject diary and remind subject to record daily medication usage including IMP, exacerbations, rescue medication or antibiotic usage, if applicable, twice daily TNSS (AM and PM) and to bring their diary to the next visit
- Pre-IMP Dietary Assessment
- Dispense IMP and administer IMP
- Commence AE reporting
- Schedule appointment for next visit

Treatment Period (Week 0 to Week 8): Subjects will take ifetroban or placebo daily for eight weeks. There will be a telephone encounter one week into this Treatment Period to ensure safety and confirm that baseline asthma symptoms have not worsened.

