#### 8.1.3 Post-treatment Period

After two weeks post-treatment, subjects will return to the site for Week 10 Post-treatment Visit.

- Record all medication use with start date and dose and check for prohibited medications.
- Inquire about AEs/SAEs
- Perform a limited physical exam with vital signs (blood pressure, heart rate, respiration rate, body temperature, weight)
- Administer TNSS, ACQ-7, and SNOT-22
- Obtain spirometry, PNIFR and FeNO
- Perform blood sampling for clinical laboratories if abnormal at Week 8 only: hematology, chemistry, PT, and INR.

- Collect urine and blood samples for eicosanoid metabolites.
- Collect nasoabsorptive matrix for eicosanoid measurements.
- Conduct a smell test (UPSIT)
- Review subject diary for content and completeness; collect data from subject diary
- Propose the optional qualitative self-assessment of the treatment to the subject

Table 8–1 Schedule of Treatment & Events

	Screening Period	Treatment Period			Post-treatment Period	
	Visit(s)	Visit	Phone Call	Visit	Visit	Visit
	Week -3 to Week 0	Week 0	Week 1	Week 4 (± 5 days)	Week 8 (± 5 days)	Week 10 (± 5 days)
Informed Consent	X					
Inclusion/Exclusion Criteria	X					
Medical & Surgical History	X					
Subject Demography	X					
Physical Exam with vital signs	X					
Limited Physical Exam with vital signs		X		X	X	X
Spirometry (FEV1)	X	X		X	X	X
PNIFR and FeNO		X		X	X	X
Pregnancy Test (Serum/Urine) a	X	X		X	X	X
Hematology b	X	X d			X	Xe
PT, INR, Chemistry c	X	X d			X	Xe
SNOT-22, TNSS, ACQ-7	$X^{\mathrm{f}}$	X		X	X	X
Smell test (UPSIT)		X		X	X	X
Collect urine & blood for eicosanoid levels		X		X	X	X
Collect nasoabsorptive matrix for eicosanoid levels		X		X	X	X
Self-assessment of the treatment (optional)					X	
Dispense IMP		X		X		
IMP Dosing	II Ontinual Once Daily Dosing (200 mg/day)I					
Record Concomitant Medications	II					
AE/SAE Recording (if any)		II				
Dispense, review and/or collect subject diary		X		X	X	X

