# 16.4 22-item Sino-nasal Outcome Test (SNOT-22)

Below you will find a list of symptoms and social/emotional consequences of your rhinosinusitis. We would like to know more about these problems and would appreciate you answering the following questions to the best of your ability. There are no right or wrong answers, and only you can provide us with this information. Please rate your problems as they have been over the past two weeks. Thank you for your participation. Do not hesitate to ask for assistance if necessary.

1. Considering how severe the problem is when you experience it and how often it happens, please rate each item below on how "bad" it is by circling the number that corresponds with how you feel using this scale: →	No Problem	Very Mild Problem	Mild or slight Problem	Moderate Problem	Severe Problem	Problem as bad as it can be	5 Most Important Items
1. Need to blow nose	0	1	2	3	4	5	0
2. Nasal Blockage	0	1	2	3	4	5	0
3. Sneezing	0	1	2	3	4	5	0
4. Runny nose	0	1	2	3	4	5	0
5. Cough	0	1	2	3	4	5	0
6. Post-nasal discharge	0	1	2	3	4	5	0
7. Thick nasal discharge	0	1	2	3	4	5	0
8. Ear fullness	0	1	2	3	4	5	0
9. Dizziness	0	1	2	3	4	5	0
10. Ear pain	0	1	2	3	4	5	0
11. Facial pain/pressure	0	1	2	3	4	5	0
12. Decreased Sense of Smell/Taste	0	1	2	3	4	5	0
13. Difficulty falling asleep	0	1	2	3	4	5	0
14. Wake up at night	0	1	2	3	4	5	0
15. Lack of a good night's sleep	0	1	2	3	4	5	0
16. Wake up tired	0	1	2	3	4	5	0
17. Fatigue	0	1	2	3	4	5	0
18. Reduced productivity	0	1	2	3	4	5	0
19. Reduced concentration	0	1	2	3	4	5	0
20. Frustrated/restless/irritable	0	1	2	3	4	5	0
21. Sad	0	1	2	3	4	5	0
22. Embarrassed	0	1	2	3	4	5	0

SNOT-20 Copyright 1996 by [name]., Washington University School of Medicine, St. Louis, MO SNOT-22 Developed from modification of SNOT-20 by National Comparative Audit of Surgery for Nasal Polyposis and Rhinosinusitis Royal College of Surgeons of England.

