### 16.7 Asthma Control Questionnaire –7 (ACQ-7)

Please answer questions 1-6. Circle the number of the response that best describes how you have been during the past week.

- 1. On average, during the past week, how often were you woken by your asthma during the night?
  - 0 Never
  - 1 Hardly ever
  - 2 A few times
  - 3 Several times
  - 4 Many times
  - 5 A great many times
  - 6 Unable to sleep because of asthma
- 2. On average, during the past week, how bad are your asthma symptoms when you wake up in the morning?
  - 0 No symptoms
  - 1 Very mild symptoms
  - 2 Mild symptoms
  - 3 Moderate symptoms
  - 4 Quite severe symptoms
  - 5 Severe symptoms
  - 6 Very severe symptoms
- 3. In general, during the past week, how limited were you in your activities because of your asthma?
  - 0 Not limited at all
  - 1 Very slightly limited
  - 2 Slightly limited
  - 3 Moderately limited
  - 4 Very limited
  - 5 Extremely limited
  - 6 Totally limited
- 4. In general, during the past week, how much shortness of breath did you experience because of your asthma?
  - 0 None
  - 1 A very little
  - 2 A little
  - 3 A moderate amount
  - 4 Ouite a lot
  - 5 A great deal
  - 6 A very great deal

- 5. In general, during the past week, how much time did you wheeze?
  - 0 Not at all
  - 1 Hardly any of the time
  - 2 A little of the time
  - 3 A moderate amount of the time
  - 4 A lot of the time
  - 5 Most of the time
  - 6 All the time
- 6. On average, during the past week, how many puffs/inhalations of short-acting bronchodilator (eg. Ventolin) have you used each day?
  - 0 None
  - 1 1-2 puffs/inhalations most days
  - 2 3-4 puffs/inhalations most days
  - 3 5-8 puffs/inhalations most days
  - 4 9-12 puffs/inhalations most days
  - 5 13-16 puffs/inhalations most days
  - 6 More than 16 puffs/inhalations most days
- 7. (To be completed by staff)

FEV, % predicted:

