 - CFB ACQ = post-treatment measurement – baseline
 - Any improvement in ACQ-7 (Yes or No): If CFB ACQ<0, then improvement =’Yes’; otherwise improvement = ‘No’
- Total Nasal Symptom Score (TNSS) AM and PM measurements
 - TNSS Daily Score = sum of the 4 symptom scores (congestion, runny_nose, nasal_itching, sneezing) for both AM and PM, separately. (listed only)
 - TNSS Visit Score: The daily score for AM and PM are averaged over time between the visits separately. Baseline Visit Score for AM and PM is obtained by averaging over the screening period and the day of the baseline visit. Week 4 Visit Score is obtained by averaging over the day after the baseline visit to the day of the Week 4 visit. Week 8 Visit Score is obtained by averaging over the day after Week 4 visit to the day of the Week 8 visit. Week 10 Visit Score is obtained by averaging over the day after Week 8 visit to the day of Week 10 visit.
 - CFB TNSS Visit Score = post-treatment measurement – baseline
- Frequency and Severity of Asthma Exacerbations (Respiratory Reaction Questionnaire)
 - Subject Frequency =count the number of reports since the previous visit for each visit
 - CFB Frequency = post-treatment measurement – baseline
 - Max Severity= define the maximum severity for each subject (none, mild, moderate, or severe) over the period since the previous visit.
 - Inhaler or rescue med (number of reports) count= count the number of reports where resp_rxn_inhaler >0 OR resp_rxn_add_tx_yn=Yes
 - CFB Inhaler or rescue= post-treatment measurement – baseline

- Frequency and Severity of Chronic Sinusitis (Sinus Infection Questionnaire)
 - Antibiotic use Frequency (number of reports) count= count the number of reports over the period since the previous visit where sinus_inf_antibio=yes
 - CFB Antibiotic use= post-treatment measurement – baseline

Pharmacodynamic Variables and biomarkers

- Plasma - Data from third party vendor
 - ScD10L (pg/mL)
 - Sp_selection (ng/mL)
- Biomarkers - Data from third party vendor.
 - Urine LTE4 (ng/mg Creatinine)
 - Urine PGD-M (ng/mg Creatinine)
 - Urine TX-M (ng/mg Creatinine)
 - Plasma F2 Isoprostanes (ng/mL)
 - Serum LTB4 (ng/mL)
 - SAM-Eicosanoids PGD2 (ng/mL)
 - SAM-Eicosanoids PXA2 (ng/mL)
 - SAM-Eicosanoids F2 Isoprostanes (ng/mL)

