5.1 Handling of Dropouts or Missing Data

Missing efficacy data which are not retrievable through queries will be imputed.

NRI

Binary response efficacy variables will be imputed by treating the missing data as a failure, ie, non-responder imputation (NRI). A response variable that is calculated from a continuous variable will only be imputed using NRI, not from the imputed continuous variable.

LOCF

Missing data for continuous efficacy variables with at least one post-baseline measurement will be imputed using Last Observation Carried Forward (LOCF). Any calculated continuous variable will be imputed after its creation.

If the baseline value is missing for any variable, then the last screening value will be used.

MI

Multiple imputation (MI) will be provided as a sensitivity analysis for the primary efficacy variable (SNOT-22 Score CFB) only. Six imputations will be calculated from PROC MI. Week 8 will be imputed using week 0 and week 4 by treatment by treatment. The analysis will be performed on the 6 imputed sets which will provide 6 estimates of LS means from separate analyses of ANCOVAs (see Section 7.1).

```
proc mi data=thedata out=outds n impute=6 seed=310
min=(-110 -110 -110 -110 -110 -110)
max=(110 110 110 110 110 110)
round=(1 1 1 1 1 1)
minmaxiter=100
noprint;
by trt;
var SNOT22BASE SNOT22CFB4 SNOT22CFB8;
run;
```

where SNOT22BASE is the baseline SNOT22 score and, SNOT22CFB4 and SNOT22CFB8 are the SNOT-22 Score values at Weeks 4 and 8, respectively.

The seed specified above will be used for development, but may be changed prior to unblinding; any such change will be documented. If convergence is not achieved with minmaxiter=100, then increase the number of iterations to 500. The properties of this approach, including convergence and collinearity, will be assessed prior to unblinding and may be adjusted to improve the operating characteristics.

After calculating the LS means of the two treatments and the estimated treatment difference and associated standard error from the ANCOVA, the 6 estimates can be placed in PROC MI analyze.

Code to obtain a single estimate of the treatment LS means and standard error.

```
proc mianalyze=thedata ; **Data output from proc mixed;  
by trt;  
modeleffects estimate; ***estimate of lsmeans for 6 sets;  
stderr stderr; *** estimate of standard error for 6 sets;  
run;
```

Code to obtain a single estimate p-value for the treatment difference.

```

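### LOCF carries on-drug scores into the Week 10 post-treatment comparisons, and the 14-day SNOT-22 recall leaves no slack for early Week 10 visits

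*Protocol*

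**What the plan says.** **Visit timing.** Protocol 8.1 states "The study visits occur on the planned dates relative to the first dose of IMP as scheduled" and allows ±5 days, which the Week 4, 8 and 10 columns of Table 8–1 repeat. Protocol 8.1.3 describes the last visit differently: "After two weeks post-treatment, subjects will return to the site for Week 10 Post-treatment Visit". The SAP schedule (4.4), written on the protocol dated 24 January 2017, shows ±2 days. On dosing, Protocol 8.1.2 says "Subjects will take ifetroban or placebo daily for eight weeks". Neither document says whether the last dose falls on day 56 or at the actual Week 8 visit.

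**Role of Week 10.** Protocol 7.1 lists a "Post-treatment period for safety and efficacy of two weeks".

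**Tests.** The SAP 7.1 chart has an ANCOVA of SNOT-22 change at Weeks 4, 8 and 10, marked LOCF/MI. SAP 7.2 adds Week 10 ANCOVAs, with LOCF, for most continuous secondary variables, and Week 10 binomial tests for improvement. Protocol 11.6.3.2 tests Weeks 4 and 8 only, and SAP section 9 does not list the Week 10 tests as a change.

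**Missing data.** SAP 5.1: "Missing data for continuous efficacy variables with at least one post-baseline measurement will be imputed using Last Observation Carried Forward (LOCF". The off-treatment visit is not excepted. Binary improvement uses non-responder imputation (NRI). Multiple imputation (MI) fills Week 8 from Weeks 0 and 4, and its code holds no Week 10 variable.

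**Recall.** SNOT-22 (Protocol 16.4): "Please rate your problems as they have been over the past two weeks". ACQ-7 (Protocol 16.7): "Circle the number of the response that best describes how you have been during the past week". For TNSS, SAP 4.6 says "Week 10 Visit Score is obtained by averaging over the day after Week 8 visit to the day of Week 10 visit".

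**The concern.** A Week 10 difference between the arms will be read as what remains after two weeks off drug. Two rules let on-drug information into it.

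The first is LOCF. A subject without a Week 10 value contributes the last score available. That may be Week 8, the End of Treatment assessments that Protocol 8.1 requires when treatment stops early, or Week 4. Each of these reflects the treatment period. The chart's LOCF/MI entry suggests a sensitivity check, but the MI described does not reach Week 10.

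The second is recall. The planned gap between Week 8 and Week 10 equals the SNOT-22 look-back, so any shorter gap means that the form rates some days on drug.

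At stake is the reading of Week 10. An effect that has gone could look as if it had partly lasted. The trial's primary conclusion is not at stake.

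**Working it through.** **1. The plan's own figure.** Inputs from SAP 4.5: difference 12, SD 16, two-sided 0.05, 90% power. n per arm = 2 × (1.960 + 1.282)² × (16/12)² = 37.4, so 38. Power with 38 per arm is 90.5% (normal) or 89.7% (noncentral t). The stated figure is reproduced. It concerns Week 8; the documents give no figure for Week 10. The standard error of the difference is 16 × √(2/38) = 3.67.

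**2. LOCF alone.** Let m be the share missing Week 10 (assumed equal by arm), 12 the on-drug difference and D the true off-drug difference. The expected error at Week 10 is m × (12 − D).

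The documents give no dropout rate, so m = 5 to 20% is an assumption:
- D = 0: 12 × 0.05 = 0.6; 12 × 0.10 = 1.2; 12 × 0.20 = 2.4 points.
- D = 6: half of these, 0.3 to 1.2 points.
- D = 12 (full persistence): no error.

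**3. SNOT-22 recall.** Gap = Week 10 day − day of last dose. On-drug recall days = max(0, 14 − gap). On the exact schedule the gap is 70 − 56 = 14, so overlap is 0. Below, every visit day in the window is equally likely and the two visits are independent (an assumption).

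| Window | Dosing ends | Gap, days | Share with overlap | Mean overlap | Worst case |
|---|---|---|---|---|---|
| ±5 | at Week 8 visit | 4–24 | 55/121 = 45% | 220/121 = 1.8 | 10 of 14 |
| ±5 | day 56 | 9–19 | 5/11 = 45% | 15/11 = 1.4 | 5 of 14 |
| ±2 | at Week 8 visit | 10–18 | 10/25 = 40% | 20/25 = 0.8 | 4 of 14 |
| ±2 | day 56 | 12–16 | 2/5 = 40% | 3/5 = 0.6 | 2 of 14 |

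With D = 0 and recall days weighted equally, the mean overlap under ±5 days adds 12 × 1.364/14 = 1.2 to 12 × 1.818/14 = 1.6 points. Under ±2 days it adds 12 × 0.6/14 = 0.5 to 12 × 0.8/14 = 0.7.

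**4. Both together.** With ±5 days and dosing to the visit, the mean overlap share is f = 1.818/14 = 0.130. Apparent difference = 12 × [m + (1 − m) × f], which is 2.1, 2.6 and 3.7 points at 5, 10 and 20% missing. With SD 16 and 38 per arm, the chance of a significant result favouring ifetroban at Week 10 rises from 2.5% to about 8%, 10% and 17%. With LOCF alone it is about 4%, 5% and 10%.

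**5. Other endpoints.**
- ACQ-7 looks back 7 days. Overlap needs a gap under 7 days, which occurs only with ±5 days and dosing to the visit: 6 of 121 pairs (5%), at most 3 of 7 days.
- TNSS at Week 10 uses only days after the Week 8 visit. If no dose is taken after that visit, LOCF is the only route.
- FEV1, PNIFR, FeNO and UPSIT are measured at the visit, so LOCF is again the only route.
- Binary improvement is not touched by LOCF, although an observed SNOT-22 improvement still carries any recall overlap.

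**The case against.** The strongest reply is that the schedule works as planned. Protocol 8.1.3 already places Week 10 two weeks after treatment, and a 14-day recall fits a 14-day gap. Overlap needs unfavourable use of the windows. Its mean effect, 1.2 to 1.6 points under ±5 days, is small beside a standard error of 3.67. The 10-of-14 case also needs dosing to continue to a Week 8 visit on day 61, although the protocol states eight weeks of dosing. No objective mentions persistence, Week 10 is not primary, and no stated decision depends on it.

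Most of this stands, and it rules out several stronger readings that a reader might infer:
- That the Week 10 comparisons are on-treatment as a matter of course. On the planned days there is no recall overlap.
- That nothing in the plan separates on-drug from off-drug data. The TNSS averaging interval and NRI do so in part.
- That ACQ-7 shares the SNOT-22 recall problem. It hardly does.
- That persistence is the sole purpose of Week 10. The documents say only safety and efficacy.

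The reply does not answer the LOCF point. That needs no unusual visit timing, only a missing Week 10 value, and the plan offers no check on it.

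**Conclusion.** The point holds, at low to moderate severity. Followed as written, the SAP analyses carried on-drug scores as Week 10 post-treatment data, and the MI analysis does not test this. If a 12-point effect vanishes off drug and missingness is 5 to 20% and equal by arm, LOCF leaves an apparent difference of 0.6 to 2.4 points. A partly lasting effect gives proportionately less. Unequal missingness could change the size or direction.

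The SNOT-22 recall overlap is a second, conditional contribution. It depends on actual visit dates, on when dosing stops and on which window applies. The 10-of-14 and 5-of-14 figures are extremes for single subjects, not trial averages. A reader might take them as the size of the bias, but the means in the table are the relevant figures, and these rest on uniform visit timing.

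The Week 8 primary analysis and its 90% power are untouched.

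**What to change.** **SAP 5.1, 7.1 and 7.2.** Do not carry values into Week 10. Make observed Week 10 data the main Week 10 analysis, and report the number missing by arm. Derive days since last dose (SAP 6.3 already uses the final-dose date for exposure) and summarise it by arm at Week 10. As a sensitivity analysis only, restrict SNOT-22 to forms completed at least 14 days after the last dose. List the Week 10 tests in SAP section 9.

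**Both documents.** Reconcile the first-dose visit anchor in Protocol 8.1 with the post-treatment wording in 8.1.3, and the ±5 days in the protocol with the ±2 days in SAP 4.4. State whether dosing ends on a fixed day or at the Week 8 visit, so that days since last dose has one meaning.

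**Cost.** One derived variable and some wording, which can be settled before unblinding. The main Week 10 analysis loses subjects: at 20% missing, 38 × 0.8 = 30.4 per arm, and the standard error rises from 3.67 to 16 × √(2/30.4) = 4.10. An observed-only analysis also assumes that Week 10 is missing for reasons unrelated to outcome. The 14-day restriction could drop about 40 to 45% of forms and selects on visit timing after randomisation, so it should not be the main analysis.
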